#### **Duration of ICU stay through Day 29**

The duration (number of days) of ICU stay from post-randomization through Day 29 will be calculated based on ICU admission and discharge dates recorded on the eCRF. Number of days in the ICU will be compared between each C19-IG 20% dose group and placebo using an ANCOVA model, including number of days in the ICU as a dependent variable, treatment group as a fixed effect, and baseline characteristics such as age and gender as covariates. From this model, the LS means and 95% CIs for each treatment group, the treatment difference in the LS

means, the 95% CI for the difference, and the associated p-value will be presented.

In the event the data is highly skewed, e.g. very few subjects admitted to ICU, a sensitivity analysis using a non-parametric Wilcoxon Rank Sum test will be performed. The p-value from Wilcoxon Rank Sum test, as wells as the Hodges-Lehmann estimate of the treatment difference and the corresponding 95% CI will be provided.

Subjects who died while in the ICU will be assigned as in the ICU for the number of days remaining from the day of death to Day 29 for the analysis. Subjects who were at ICU at study completion will be assigned an ICU end date equals to the date of completion for the purpose of deriving the number of ICU days. Subjects who never been in the ICU through Day 29 will be included in the analysis with a value of zero days in the ICU.

#### Proportion of subjects requiring invasive mechanical ventilation through Day 29

The proportion of subjects requiring invasive mechanical ventilation through Day 29 within each treatment group will be presented along with a two-sided exact (Clopper-Pearson) 95% CI.

The observed difference in the proportion of subjects requiring invasive mechanical ventilation between each C19-IG 20% dose group and placebo along with the exact unconditional 95% CI for risk difference will be calculated. The null hypothesis will be tested using Chi-square statistic and the p-value will be reported.

#### Duration of invasive mechanical ventilation through Day 29

The duration (number of days) on invasive mechanical ventilation from post randomization through Day 29 will be calculated based on the start/stop dates of invasive mechanical ventilation recorded on the eCRF All Visits page "General Duration of Hospitalization, & Overall Requirement for Mechanical Ventilation, ICU Admission and/or Oxygen Supplementation". Number of days on invasive mechanical ventilation will be compared between each C19-IG 20% dose group and placebo using an ANCOVA model, including number of days in on invasive mechanical ventilation, treatment group as a fixed effect, and baseline characteristics such as age and gender as covariates. From this model, the LS means and 95% CIs for each treatment group, the treatment difference in the LS means, the 95% CI for the difference, and the associated p-value will be presented.

In the event the data is highly skewed, e.g. very few subjects on invasive mechanical ventilation, a sensitivity analysis using a non-parametric Wilcoxon Rank Sum test will be performed. The p-value from Wilcoxon Rank Sum test, as wells as the Hodges-Lehmann estimate of the treatment difference and the corresponding 95% CI will be provided.

Subjects who died during the hospitalization without a stop date of invasive mechanical ventilation recorded on the eCRF will be assigned as being on mechanical ventilation for the number of days remaining to Day 29 for the analysis. Subjects who had invasive mechanical ventilation ongoing at study completion will be assigned a mechanical ventilation end date equals to the date of completion for the purpose of deriving duration of mechanical ventilation. Subjects who are never placed on invasive mechanical ventilation through Day 29 will be included in the analysis with a value of zero days on mechanical ventilation.

Data collected on "Respiratory Support" eCRF through Day 60/Final Phone Check visit will be presented in a listing.

#### Mortality rate through Day 29

Subject status (Alive/Death) will be recorded in the database. If the vital status of the subject is missing, then the subject will be treated as death for the analysis.

The proportion of subjects who die through Day 29 within each treatment group will be presented along with a two-sided exact (Clopper-Pearson) 95% CI.

The observed difference in the mortality rate (proportion of deceased subjects) between each C19-IG 20% dose group and placebo along with the exact unconditional 95% CI for risk difference will be calculated. The null hypothesis will be tested using Chi-square statistic and the p-value will be reported.

Subject status after Day 29 (vital status [living or deceased], any hospital admissions, ICU admissions, requirement for invasive mechanical ventilation, need for oxygen supplementation) collected at Day 60/Final Phone Check visit will be presented in a listing.

#### Proportion of subjects with critical COVID-19 illness through Day 29

Critical COVID-19 illness is defined as any of the following: (a) requiring ICU admission or ICU level of care, (b) invasive mechanical ventilation, or (c) resulting in death by Day 29.

The proportion of subjects with critical COVID-19 illness defined above within each treatment group will be presented along with a two-sided exact (Clopper-Pearson) 95% CI.

The observed difference in the proportion of subjects with critical COVID-19 illness between each C19-IG 20% dose group and placebo along with the exact unconditional 95% CI for risk difference will be calculated. The null hypothesis will be tested using Chi-square statistic and the p-value will be reported.

#### Time to clinical progression (critical COVID-19 illness) through Day 29

Clinical progression is defined as death, start of invasive mechanical ventilation, or ICU admission/requiring ICU level of care through Day 29, whichever occurs first. The time to clinical progression will be estimated using the KM method. The KM estimates along with 95% CI, and survival curves will be provided. Based on the KM estimates, the probabilities of experiencing clinical progression and associated 95% CIs on Days 14 and 29 will be reported; in addition, the 25%, 50% (median), and 75% percentiles of the time to clinical progression with associated 95% CIs will be provided, as data permit. The survival rates between each C19-IG 20% dose group and placebo will be compared using Log-rank test. The p-value from Log-rank test will be presented.

#### Time to COVID-19 symptoms through Day 14

Time to COVID-19 symptoms is defined as the time from study drug administration to the first time point when any element of the case definition for primary efficacy variable is fulfilled through Day 14. The time to COVID-19 symptoms will be estimated using the KM method. The KM estimates along with 95% CI, and survival curves will be provided. Based on the KM estimates, the probabilities of experiencing COVID-19 symptoms and associated 95% CIs at Day 14 will be reported; in addition, the 25%, 50% (median), and 75% percentiles of the time to COVID-19 symptoms with associated 95% CIs will be provided, as data permit. The survival rates between each C19-IG 20% dose group and placebo will be compared using Log-rank test. The p-value from Log-rank test will be presented.

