#### 7.2.3 Day 3 Healthcare Provider Visit

Assessments include the following:

- Ordinal Scale assessment
- NEWS (Appendix 2)
- Surveillance for COVID-19 symptoms (detailed checklist) including: fever, cough, shortness of breath, fatigue, myalgia etc.
- Vital signs (temperature, systolic and diastolic blood pressure, pulse, respiratory rate)
- Record oxygen saturation (specify on or off oxygen supplementation)
- Record any Medically Attended Visit(s) for management/treatment of COVID-19 (other than routine study-directed visits) in any setting, specifying type (eg, Emergency department, urgent care, outpatient clinic/professional setting for direct inperson/telemedicine medical assessment and care of COVID-19 provided by licensed healthcare personnel)
- If subject requires supplemental oxygen post randomization: Record any supplemental oxygen administration (type, %, flow start/end date/time)
- If subject requires hospital admission post randomization: Record hospital admission and discharge dates
- If subject requires ICU admission post randomization: Record ICU admission and discharge dates
- If subject requires invasive mechanical ventilation post randomization: Record details of invasive mechanical ventilation parameters (start/end date/time)
- Respiratory sample for quantitative measurement of SARS-CoV-2 viral load by NAT or PCR (real-time RT-PCR) (obtained via nasopharyngeal swab)
- Record SAEs and TEAEs
- Record concomitant medications

	Number	BIG-CL-PRT-000028	Version	2.0	Status	Effective	Effective Date	13-Oct-2021
VILOL2	GC2010 - A	Multicenter, Randomized, Double-blind,	, Parallel Gro	up Study to E	aluate the Saf	ety and Efficacy of		3013-02
and Colored	Anti-COVID-19 Immune G	lobulin (Human) 20% (C1	19-1G 20%) ve	rsus Placebo	in Asymptoma	ic Ambulatory	rage	OOL 10 07

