#### 4.6 Data Derivations and Transformations

The following derivations will be used in this study:

Study Day:

- Date of assessment date of study drug administration + 1 for assessments done on or after date of study drug administration
- Date of assessment date of study drug administration for assessments done before date of study drug administration

Baseline Observation: the last non-missing value prior to study drug administration.

Duration:

• Duration in days = end date - start date + 1

• Duration in minutes = end time in minutes – start time in minutes

Origin or Start Date for Time to Event Endpoints:

- Time to negative SARS-CoV-2 by PCR: date of study drug administration
- Time to Clinical Progression: date of study drug administration
- Time to COVID-19 symptoms through Day 14: date of study drug administration

Event Date for Time to negative SARS-CoV-2 by PCR:

• The date of the first negative result from the SARS-CoV-2 assessment by PCR will be used as the event date for deriving time to negative SARS-CoV-2.

Event Date for Time to Clinical Progression

• The event date will be the date of death, the start date of invasive mechanical ventilation, or the date of ICU admission/requiring ICU level of care, whichever occurs first.

Event Date for Time to COVID-19 symptoms through Day 14

• The event date will be the first time point when any element of the case definition for primary efficacy variable is fulfilled through Day 14

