The proportion of subjects requiring oxygen supplementation through Day 29 within each treatment group will be presented along with a two-sided exact (Clopper-Pearson) 95% CI.

The observed difference in the proportion of subjects requiring oxygen supplementation between each C19-IG 20% dose group and placebo along with the exact unconditional 95% CI for risk difference will be calculated. The null hypothesis will be tested using Chi-square statistic and the p-value will be reported.

### Duration of any oxygen use through Day 29

The duration (number of Days) of any oxygen use from Day 1 through Day 29 will be calculated based on the start/stop date of using oxygen supplementation recorded on the eCRF All Visits page "General Duration of Hospitalization, & Overall Requirement for Mechanical Ventilation, ICU Admission and/or Oxygen Supplementation". Number of days on oxygen will be compared between each C19-IG 20% dose group and placebo using an ANCOVA model, including number of days on oxygen as a dependent variable, treatment group as a fixed effect, and baseline characteristics such as age and gender as covariates. From this model, the LS means and 95% CIs for each treatment group, the treatment difference in the LS means, the 95% CI for the difference, and the associated p-value will be presented.

In the event the data is highly skewed, e.g. very few subjects received supplemental oxygen, a sensitivity analysis using a non-parametric Wilcoxon Rank Sum test will be performed. The p-value from Wilcoxon Rank Sum test, as wells as the Hodges-Lehmann estimate of the treatment difference and the corresponding 95% CI will be provided.

Subjects who died during the hospitalization without a stop date of using oxygen supplementation recorded on the eCRF will be assigned as being on oxygen for the number of days remaining to Day 29 for the analysis. Subjects who had oxygen use ongoing at study completion will be assigned an oxygen use end date equals to the date of completion for the purpose of deriving duration of oxygen use. Subjects who never received supplemental oxygen through Day 29 will be included in the analysis with a value of zero days of oxygen use.

A listing of all supplemental oxygen and saturation (SpO2 and SaO2) data collected from both subject self-monitoring at home and health provider visits will be provided.

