### **Duration of Hospitalization through Day 29**

The duration (number of days) of hospitalization from post-randomization through Day 29 will be calculated based on hospital admission and discharge dates recorded on the eCRF. Number of days in the hospital will be compared between each C19-IG 20% dose group and placebo using an ANCOVA model, including number of days in the hospital as a dependent variable, treatment group as a fixed effect, and baseline characteristics such as age and gender as covariates. From this model, the LS means and 95% CIs for each treatment group, the treatment difference in the LS means, the 95% CI for the difference, and the associated p-value will be presented.

In the event the data is highly skewed, e.g. very few subjects hospitalized, a sensitivity analysis using a non-parametric Wilcoxon Rank Sum test will be performed. The p-value from Wilcoxon Rank Sum test, as wells as the Hodges-Lehmann estimate of the treatment difference and the corresponding 95% CI will be provided.

Subjects who died while in the hospital will be assigned as in the hospital for the number of days remaining from the day of death to Day 29 for the analysis. Subjects who were in the hospital at study completion will be assigned a hospitalization end date equals to the date of completion for the purpose of deriving the duration of hospitalization. Subjects who never been hospitalized through Day 29 will be included in the analysis with a value of zero days in the hospital.

#### Proportion of subjects requiring ICU admission through Day 29

The proportion of subjects requiring ICU admission through Day 29 within each treatment group will be presented along with a two-sided exact (Clopper-Pearson) 95% CI.

The observed difference in the proportion of subjects requiring ICU admission between each C19-IG 20% dose group and placebo along with the exact unconditional 95% CI for risk difference will be calculated. The null hypothesis will be tested using Chi-square statistic and the p-value will be reported.

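### Oxygen and ventilation days run to Day 29 after death only if the stop date is blank, so entering the date of death as the stop date shortens the count

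*SAP*

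**What the plan says.** SAP 6.2 analyses four durations through Day 29: oxygen, hospital stay, ICU stay and invasive ventilation. Each has its own rule for subjects who die.

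- Hospital stay: "Subjects who died while in the hospital will be assigned as in the hospital for the number of days remaining from the day of death", through Day 29. The only condition is where the death occurred.
- ICU stay: "Subjects who died while in the ICU will be assigned as in the ICU for the number of days remaining from the day of death", again through Day 29 and with no further condition.
- Oxygen: the extension is confined to this group: "Subjects who died during the hospitalization without a stop date of using oxygen supplementation recorded on the eCRF".
- Invasive ventilation: the same restriction, "Subjects who died during the hospitalization without a stop date of invasive mechanical ventilation recorded on the eCRF". These subjects "will be assigned as being on mechanical ventilation for the number of days remaining to Day 29 for the analysis".

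SAP 4.6 gives the general derivation: "Duration in days = end date - start date + 1". Subjects who never had the support, or were never admitted, enter each analysis as zero days.

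On data collection, Protocol 7.2.3 and the later contact sections tell sites: "Record details of invasive mechanical ventilation parameters (start/end date/time"). The oxygen instruction also asks for start and end date and time. Neither says what to enter when the subject dies on support.

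**The concern.** Fewer days is the better result on all four endpoints. Without a special rule, an early death on support would look like an early recovery, and running the count to Day 29 prevents that. For hospital and ICU days the protection does not depend on how the form is completed. For oxygen and ventilation days it depends on whether one date field is empty. A site that closes the support record with the date of death, which is a natural way to answer a request for an end date, removes the protection.

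Two subjects with identical courses can then receive very different durations. A death on support can score better than survival with longer support. One subject's ventilation days can also disagree with the same subject's hospital days for no clinical reason.

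**Working it through.** The documents give no figure for this rule, so there is nothing to reproduce. The check applies the SAP's own formula to assumed dates.

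**Inputs.** Duration formula: end minus start plus 1 (SAP 4.6). Death rules: SAP 6.2, as set out above. Arm size: 267 randomized, about 240 after the planned 10% withdrawal (SAP 10). Days of start and death: assumed.

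**Which rule applies.** A subject who dies on ventilation with a stop date entered fails the condition in the ventilation rule. The other special rules in that section cover support still running at study completion and subjects never ventilated; neither fits. That leaves the general formula. The same holds for oxygen.

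**One subject.** Ventilation starts on Day 8, death in hospital on Day 10.

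- Stop date entered as Day 10: 10 − 8 + 1 = 3 days.
- Stop date blank, counted to Day 29: 29 − 8 + 1 = 22 days.
- Gap: 22 − 3 = 19 days = 29 − 10.
- Hospital days, if admitted on Day 8: 22 under either form entry.
- Assumed comparator, a survivor ventilated from Day 8 to Day 17: 17 − 8 + 1 = 10 days. The death scores 3, which is better than 10; under the Day 29 rule it scores 22, which is worse.

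**Range of dates.** The start day cancels, so the gap is always 29 minus the day of death.

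| Start day | Death day | Stop date = date of death | Stop date blank | Gap |
|---|---|---|---|---|
| 5 | 6 | 2 | 25 | 23 |
| 5 | 8 | 4 | 25 | 21 |
| 8 | 10 | 3 | 22 | 19 |
| 10 | 14 | 5 | 20 | 15 |
| 10 | 20 | 11 | 20 | 9 |
| 14 | 28 | 15 | 16 | 1 |

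**Arm mean.** One death with a 19-day gap moves the mean by 19/240 = 0.079 day (19/267 = 0.071 with all randomized subjects). Five deaths with a 21-day gap move it by 5 × 21/267 = 0.39 day. Because unsupported subjects enter as zeros, the means are themselves small. If the Day 8 to Day 10 subject were the only ventilated one among 240, the arm mean would be 3/240 = 0.0125 or 22/240 = 0.092 day, about a seven-fold difference from one field.

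**The case against.** The strongest defence is that the condition has a purpose. A subject weaned before dying has a genuine stop date; one who died on support has none. The blank field may be meant to separate the two. The purpose is sound, but the wording does not secure it, because a stop date equal to the date of death is treated like genuine weaning. The need for a clarification stands.

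A reader might infer that sites following instructions will trigger the problem. The documents do not establish that. The eCRF completion guidelines are not among them, and if they tell sites to leave the field blank at death, the rule works as intended.

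A reader might also infer that death is scored as a good outcome. That goes too far. A subject ventilated for 3 days who then dies still scores worse than every never-ventilated subject and still adds to the arm mean. In the rank-sum analysis, 3 rather than 22 changes the order only against other ventilated subjects with values in that range.

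Death is also captured elsewhere: all-cause mortality, critical illness, time to clinical progression, and the worst category of the ordinal scale. A mortality imbalance would not be hidden by a duration table.

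Finally, a death at home without admission gets zero hospital days: "Subjects who never been hospitalized through Day 29 will be included in the analysis with a value of zero days in the hospital". A reader might call this the same fault. It is not. Zero is the literal count for an endpoint worded around subjects who are admitted, and scoring such a death as hospital days would be a choice of estimand rather than the repair of an error.

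**Conclusion.** The concern holds as an inconsistency among the four death rules in SAP 6.2. It depends on one assumption, that some sites enter the date of death as the stop date; the protocol text permits this but does not direct it. Where it happens, the count for that subject falls by 29 minus the day of death: large for early deaths, nearly nil for deaths close to Day 29.

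The consequence is modest. Oxygen and ventilation durations are secondary endpoints, and SAP 4.5 makes no multiplicity adjustment for them. The shift is about 0.08 day in an arm mean per death in the worked case, and the documents give no expected number of such deaths. The primary result is not affected.

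Both durations appear in the interim list in SAP 9, so a reader might infer that the futility decision is at risk. The documents do not support that step: the decision rests on conditional power for the primary outcome together with an unweighted look at many secondary outcomes, and no threshold is attached to either duration.

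**What to change.** In the oxygen and ventilation paragraphs of SAP 6.2, replace the condition on a blank stop date with status at death:

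- Any subject who dies on or before Day 29 with the stop date missing or equal to the date of death is counted from the start of that support through Day 29.
- A subject who came off support before the day of death keeps the recorded stop date.

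This brings the two rules into line with the hospital and ICU rules and keeps the distinction that the present condition probably aims at. It also covers a death on oxygen outside hospital, which the present rule leaves out. No separate rule for scoring deaths outside hospital as hospital days is needed.

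The cost is a sentence or two of SAP text and one derivation change for each endpoint. Mean durations become slightly longer in any arm with such deaths. The change should be made before anyone sees deaths by arm, so that the choice cannot be driven by the data.

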#### 5.3.4 Follow-up of Subjects Withdrawn from Study

For subjects administered any amount of blinded IP who discontinue the clinical trial details for follow-up are delineated below.

For subjects who withdraw from the clinical trial (excluding screen failures), study procedures and assessments scheduled for the Day 14 Visit will be performed at the time of withdrawal, during an unscheduled visit at the time of withdrawal. In addition, to assure major clinical outcomes are adequately captured as a measure of overall safety, these subjects will be asked to attend their chronological Day 29 Healthcare Provider Visit (ie, 28 days after Day 1 baseline), unless the unscheduled visit is within 4 days of their chronological Day 29 visit, and provided that they or their legally acceptable representative have not withdrawn consent. At the chronological Day 29 Healthcare Provider Visit, all assessments will be performed. These subjects will also have a Phone Checks on Day 60 as follow-up after the Day 29 Final Healthcare Provider Visit.

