### 4.4 Handling of Dropouts or Missing Data

Missing data will be treated as missing and no method for imputation is planned for study population or safety analyses except for the partial end dates/times for concomitant medications (Section 5.6) and partial onset dates/times for AEs (Section 7.2.1). When applicable, missing data for binary and selected continuous efficacy endpoints will be imputed using a most conservative/worst case approach, and the related details are described in Section 6.

Missing data on the time to event endpoints will have events coded as right censored per the

following table:

Endpoint	Right Censoring
Time to negative SARS-CoV-2 by PCR	Subjects who did not have negative SARS-CoV-2 by PCR will be right censored as of the date of last non-missing assessment of SARS-CoV-2 by PCR on or prior to Day 29.
Time to Clinical Progression (death, invasive mechanical ventilation, or ICU admission/requiring ICU level of care)	Subjects who did not meet the criteria for clinical progression will be right censored as of the date of last subject contact on or prior to Day 29.
Time to COVID-19 symptoms (fulfillment of the case definition used for the primary efficacy variable through Day 14)	Subjects who did not meet the criteria will be right censored as of the date of last non-missing assessment of clinical features/symptoms on or prior to Day 14.

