### 9. INTERIM FUTILITY ANALYSIS

An interim analysis will be conducted in the December 2021 timeframe based on all available data assessable for the primary endpoint and key secondary efficacy endpoints to assess whether the trial will be terminated due to lack of efficacy (futility). The unblinded output will be reviewed by an independent unblinded team, and the study team will remain blinded.

The decision for the interim analysis will be based on the conditional power (the power conditional on the observed data accumulated at the interim analysis) for the primary outcome, as well as assessment of the secondary efficacy outcomes.

The futility analysis will include for the primary efficacy endpoint variable, all patients with data through Day 14, and for the following secondary efficacy endpoint variables, all patients with data through Day 14 or Day 29, as specified for each endpoint:

- Time to COVID-19 symptoms specifically defined as the time to fulfillment of the case definition used for the primary efficacy variable through Day 14.
- Proportion of subjects who remain in an outpatient setting and maintain SpO2 ≥94% on room air on Day 3, Day 7, and Day 14.
- Proportion of subjects who require O2 supplementation on or before Day 29.
- If requiring supplemental oxygen post randomization: Duration of any oxygen through Day 29.
- Absolute value and mean change from baseline in the 7-point Ordinal scale at Day 1, Day 7, Day 14, and Day 29
- Proportion (percentage) of subjects in each severity category of the 7-point Ordinal scale at Day 1, Day 7, Day 14, and Day 29.
- Assessment of Clinical Severity: Change in NEWS from baseline (at Day 7, Day 14, and

Day 29).

- Proportion who require at least one COVID-19 related medically attended visit for management/treatment of COVID-19 (apart from routinely scheduled study-directed visits) which may occur in any setting through Day 29 (e.g., Emergency department, urgent care, outpatient clinic or professional setting wherein direct in-person/telemedicine medical assessment and escalation of care for COVID-19 is provided by licensed healthcare personnel).
- Proportion of subjects who require hospital admission for medical care (non-quarantine purposes) through Day 29.
- If admitted to hospital post randomization: Duration of hospital stay through Day 29.
- Proportion of subjects who require ICU admission or initiation of ICU-level care\* through Day 29.

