### **10. SAMPLE SIZE AND POWER CALCULATIONS**

Because of the urgency and lack of previous prospective COVID-19 data, sample size estimation remains incompletely defined; however, the size of this study is commensurate with other Phase 3 investigations ongoing during the COVID-19 pandemic.

For overall context, one may reference the mAb data for casirivimab and imdevimab (Regeneron cocktail) in support of their Emergency Use Authorization (EUA) granted 20 November 2020. The R10933-10987-COV-2067 study on which the data analysis for the EUA was based included 799 enrolled subjects (~266/arm).

If it is assumed that 80% of patients in the Placebo control arm will remain asymptomatic at Day 14 (subset of ~314 patients PCR + at baseline) then the sample size projections in the table below emerge for various degrees of C19-IG 20% treatment effect (delta).

Practically speaking then the sample size becomes ~240 patients/arm for a significance level alpha (0.025) and 80% power (Table 2). Assuming a 10% withdrawal rate, 267 patients per arm would be needed. Furthermore, this calculation provides a per group sample size commensurate with the per arm group size supporting Regeneron's EUA for casirivimab and imdevimab.

Control Success % (proportion remaining Asymptomatic ) (reference)	Absolute Delta C19-IG 20%			20% Success % ion remaining matic )	Sample Size (total)		
80% (Mitja et al., NEJM 2020)	5%	10%	85%	90%	1094/arm	238/arm	

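### Counting every missing vital status as a death inflates Day 29 mortality and lets unequal loss to follow-up pass as a mortality difference

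*SAP*

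**What the plan says.** SAP 6.2, under the mortality rate through Day 29, sets the rule: "If the vital status of the subject is missing, then the subject will be treated as death for the analysis". The same subsection then reports the proportion dead per arm with a Clopper-Pearson interval, the risk difference from placebo with an exact unconditional interval, and a chi-square p-value. This carries out the general rule in SAP 4.4 that "missing data for binary and selected continuous efficacy endpoints will be imputed using a most conservative/worst case approach".

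Other parts of the plan bear on the same subjects:

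- **Time to clinical progression** includes death as an event. Under SAP 4.4, subjects without an event "will be right censored as of the date of last subject contact on or prior to Day 29".
- **Critical COVID-19 illness** (SAP 6.2) has as one component "c) resulting in death by Day 29". It does not say whether imputed deaths count.
- **Status after Day 29** (SAP 6.2), when "collected at Day 60/Final Phone Check visit will be presented in a listing", has no stated role in settling a missing Day 29 status.
- **Withdrawn subjects** (Protocol 5.3.4): where consent has not been withdrawn, "these subjects will be asked to attend their chronological Day 29 Healthcare Provider Visit", and they also receive the Day 60 call.
- **Sample size** (SAP 10): "Assuming a 10% withdrawal rate, 267 patients per arm would be needed". No mortality rate is assumed anywhere.

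**The concern.** A worst-case imputation is conservative when it works against the treatment claim. Applied alike to all arms, it has no fixed direction: it converts lost contacts into deaths, so the arm with more lost contacts looks worse, whichever arm that is.

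The population makes this matter. Subjects enter as asymptomatic outpatients, so Day 29 mortality may well be low. Once the share with missing status exceeds true mortality, most of the counted deaths are not deaths.

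The plan is also inconsistent with itself. The same lost subject is dead in one Day 29 secondary endpoint and censored alive in another. Read literally, a subject who misses Day 29 but answers the Day 60 call could be counted as dead.

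All-cause mortality is a tested secondary endpoint that readers will take at face value, and no mortality-rate analysis without the imputation is planned.

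**Working it through.** **Inputs from the documents.** 267 per arm (SAP 3.1); two-sided 5% tests (SAP 4); chi-square for each dose against placebo (SAP 6.2); 10% withdrawal (SAP 10).

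**Assumed inputs.** True Day 29 mortality *d* from 0% to 2%, and missing share *m* from 1% to 10%, unrelated to death. The 10% is a withdrawal allowance, so it is an upper-end value for missing vital status. All 267 per arm are taken as dosed.

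**The plan's own figure.** There is none for mortality. The sample size does reproduce. With alpha 0.025 two-sided and 80% power, the unpooled two-proportion formula for 80% versus 90% gives 237.6, hence the stated 238. Dividing the rounded 240 by 0.90 gives 267. That part is not in dispute.

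**Step 1: rate reported under the rule.** Analysed rate = *d* + (1 − *d*)*m*. For *d* = 1% and *m* = 2%: 0.01 + 0.99 × 0.02 = 2.98%, about three times the truth. For *d* = 0.5% and *m* = 10%: 0.005 + 0.995 × 0.10 = 10.45%, about 21 times the truth.

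**Step 2: share of counted deaths that are imputed.** (1 − *d*)*m* / [*d* + (1 − *d*)*m*]. For *d* = 1% and *m* = 2%: 0.0198 / 0.0298 = 66%.

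| True mortality | 1% missing | 2% missing | 5% missing | 10% missing |
|---|---|---|---|---|
| 0.5% | 67% | 80% | 91% | 95% |
| 1% | 50% | 66% | 83% | 91% |
| 2% | 33% | 49% | 71% | 83% |

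**Step 3: smallest imbalance that reaches significance.** Take no deaths and 4 versus 0 missing statuses. The reported rates are 4/267 = 1.5% and 0%. The pooled rate is 4/534 = 0.00749, and z = 0.01498 / √(0.00749 × 0.99251 × 2/267) = 2.01, p = 0.045. Three versus 0 gives p = 0.082.

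**Step 4: chance of a significant mortality difference with no deaths.** This sums the exact joint binomial distribution (267 versus 267) over the rejection region of the uncorrected chi-square test.

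| Missing in the two arms | Probability of p < 0.05 |
|---|---|
| 2% vs 1.5% | 7% |
| 3% vs 2% | 11% |
| 2% vs 1% | 14% |
| 3% vs 1% | 38% |
| 10% vs 5% | 60% |

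**Step 5: equal loss.** For *m* from 1% to 10%, with *d* = 0 or 1% in both arms, the rejection probability is 4.6% to 5.1%, so the type I error holds. The effect is diluted. For true mortality of 2% versus 1% (risk ratio 0.50), the reported ratio is (0.01 + 0.99*m*) / (0.02 + 0.98*m*):

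| Missing in both arms | Reported rates | Reported risk ratio |
|---|---|---|
| 1% | 2.98% vs 1.99% | 0.67 |
| 2% | 3.96% vs 2.98% | 0.75 |
| 5% | 6.90% vs 5.95% | 0.86 |
| 10% | 11.80% vs 10.90% | 0.92 |

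For 2% versus 0.5%, power falls from 33% with none missing to 16% at 2% missing.

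**The case against.** The strongest reply is that the harm is conditional and probably small. Inflation needs living subjects with missing status, and bias between arms needs unequal loss. Dosed subjects are contacted on Days 3, 5, 7, 9, 11, 14 and 29, withdrawn subjects are asked back, and a Day 60 call follows. Nothing in a double-blind, single-dose trial with matched volumes makes a twofold difference in loss likely. This stands. It is why 10% is only an upper-end value and the range starts at 1%, but the problem is already present at 1%.

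Second, the 4 versus 0 example leans on a sparse-table test. Fisher's exact test gives p = 0.124, and the 2% vs 1% probability drops from 14% to 8%. That is correct arithmetic, but SAP version 2.0 replaced Fisher's test with chi-square throughout the efficacy section, so chi-square is what would be reported. Under Fisher's test, 10% vs 5% missing still gives 54%.

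Third, the SAP does not forbid using a Day 60 contact to settle Day 29 status. True, but it does not provide for it either.

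Fourth, recorded deaths appear in the table of adverse events leading to death, in ordinal category 1 and in time to clinical progression. None of these is a Day 29 mortality rate compared between arms.

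Fifth, missing-as-failure is a familiar, transparent convention, while Kaplan-Meier censoring assumes that loss is unrelated to death. Both points are fair. They support keeping the worst case as a sensitivity analysis, not as the only analysis. Power is low in any case: for 2% versus 1% it is 14% with complete data. The main damage is therefore to the reported rate and to false differences, not to lost inference.

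**Conclusion.** The concern holds and should be fixed. The rule is explicit, applies to every arm, and governs the only Day 29 mortality-rate analysis. The rate is too high whenever any subject with missing status is alive. With unequal loss, the comparison favours the better-followed arm. With equal loss, the test keeps its size but the effect is pulled toward no difference.

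How much this matters rests on two quantities that the documents do not give, true mortality and the missing share. At 1% mortality and 1% to 2% missing, half to two thirds of counted deaths would be imputed, and an imbalance of four lost contacts is enough for p < 0.05 if nobody dies.

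The consequence is limited to a secondary endpoint outside the multiplicity hierarchy and, if imputed deaths are carried over, to the critical-illness composite. Exposure at the futility look is small, because SAP 9 takes for each secondary endpoint "all patients with data through Day 14 or Day 29, as specified for each endpoint".

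**What to change.** In SAP 6.2, replace the sentence on missing vital status as follows:

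1. Count observed deaths through Day 29.
2. Treat a subject as alive at Day 29 if any later contact, including the Day 60 phone check, shows it.
3. Otherwise censor at last contact and compare Day 29 Kaplan-Meier mortality, as the SAP already does for clinical progression.
4. Keep missing-as-death as a labelled sensitivity analysis, and report the number with missing vital status per arm beside it.
5. Use the same observed-death definition in the critical COVID-19 illness composite.

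This changes SAP wording only. It uses contact dates and Day 60 status that are already collected, and the worst-case view is kept. It should be settled before unblinding.
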